## SUMMARY

This is a randomized, double-blind, placebo-controlled, parallel-group, study evaluating the effect of a Qualia Vitamin C+ formulation on Whole Blood Vitamin C levels in the blood of healthy adults aged 25 years or older. Approximately 36 participants will be randomized to one of two study arms: Qualia Vitamin C+ or placebo. Each participant will take two capsules of their assigned product once daily in the morning, with or without food, over a 28-day period. The primary outcome is the change in blood vitamin C levels, assessed via in lab blood collection at baseline and study completion. Secondary endpoints include questionnaires measuring health-related cognitive functioning and stress (PROMIS Cognitive Function - Short Form 8a and the Perceived Stress Scale-10), the Single-item Assessment of Immune Fitness, evaluation of safety and tolerability, and an Overall Experience Questionnaire (Appendices 1, 4-7). All assessments, including electronic questionnaires, are completed remotely without in-person visits.

## OUTCOMES

### Primary Objective

To assess between-group differences in the change in blood Vitamin C levels from baseline to Day 28 following supplementation with Qualia Vitamin C+ versus placebo.

### Secondary Objectives

To assess within-group and between-group differences in PROMIS Cognitive Function - Short Form 8a, Perceived Stress Scale-10 domain scores, and Single-item Assessment of Immune Fitness.

To assess within-group differences in the change in blood Vitamin C levels.

To evaluate side effect profiles using a custom Safety and Tolerability survey.

---

# STRATIFICATION

Participants will be stratified by gender and age at screening before being randomly assigned in a 1:1 ratio to one of the two study arms (Qualia Vitamin C+ or placebo). Each participant will have an equal probability of receiving either Qualia Vitamin C+ or placebo.

---

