# NUMBER OF PARTICIPANTS

Number of Participants: Approximately 36 total (18 in each arm)

---

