## METHODS

### Study Design

Design: Randomized Double-Blind Placebo-Controlled Parallel Trial (2 arms) with 1:1 allocation, stratified by gender and age.

Arms: (1) Qualia Vitamin C+, and (2) Placebo

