## Statistical Methodology

Data will be assessed for normality using the Shapiro-Wilk test and by evaluating skewness and kurtosis. Descriptive statistics will be reported as mean (SD) for continuous variables and frequencies (percentages) for categorical variables. For each outcome, changes from baseline will be computed at subsequent time points, and paired t-tests or linear mixed-effects models will be used to evaluate within-group differences. Between-group comparisons will be conducted using linear mixed-effects models with fixed effects for group, time, and their interaction, and a random intercept for participants to account for repeated measures. Data that do not meet the assumptions of normality will be analyzed using appropriate non-parametric statistical tests. Estimated coefficients, 95% confidence intervals, and p-values for interaction terms will be extracted at each time point. Moderator variables will be considered in adjusted models. Analyses will be performed using Python (statsmodels). The sample size was estimated to yield 80% power to detect an effect size (Cohen's  $d = 0.80$ ) with a two-tailed t-test at a 0.05 significance level.

---

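### Randomisation is stratified by gender and age, but the stated between-group model commits to neither; if either predicts change in the outcome, the test is conservative and precision is left unused

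*Combined protocol and SAP*

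**What the plan says.** The protocol states the stratification twice. The Stratification section says "Participants will be stratified by gender and age at screening before being randomly assigned", and Study Design repeats it: "with 1:1 allocation, stratified by gender and age". Neither place gives age bands.

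The Primary Objective is a contrast of changes: "To assess between-group differences in the change in blood Vitamin C levels from baseline to Day 28". Statistical Methodology makes the between-group comparisons with "linear mixed-effects models with fixed effects for group, time, and their interaction, and a random intercept for participants". Gender and age are not in that list.

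The only mention of adjustment is "Moderator variables will be considered in adjusted models". It does not name the moderators, say how they would enter the model, or say whether an adjusted or an unadjusted result is primary. Number of Participants gives 18 per arm.

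**The concern.** Stratifying makes the arms alike on gender and age, so the treatment estimate varies less from trial to trial wherever those factors predict the analysed quantity. A model that omits them still counts their contribution as residual noise. The reported standard error is then larger than the true one, the interval is too wide, and the test rejects less often than its nominal level. With 18 per arm there is little precision to spare.

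The moderator sentence adds a second problem. It leaves an adjusted and an unadjusted answer both available, with nothing to say which one counts.

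**Working it through.** **Inputs from the documents.** 18 per arm (Number of Participants); d = 0.80, two-sided t-test, alpha 0.05, 80% power claimed (Statistical Methodology). No SD is given, so the total within-arm SD of change is set to 1.

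**Assumed input.** R² is the share of the within-arm variance in change explained by gender and age. The documents give no value, so 0 to 0.30 is shown.

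**Step 1: the plan's own figure.** An unadjusted two-sample t-test with 18 per arm has noncentrality 0.80 × √(18/2) = 2.40 on 34 df. Exact power is 64.5%, not 80%. That shortfall is a separate matter; 64.5% is the reference point here.

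**Step 2: effect of omitting the stratifiers in an analysis of change.** With arms balanced within strata:
- Unadjusted SE divided by true SE is about 1/√(1 − R²).
- The unadjusted test therefore behaves as if its critical value were 2.032/√(1 − R²) in place of 2.032, which gives its true alpha.
- Adjusted power uses noncentrality 2.40/√(1 − R²) on 36 − 2 − 2 = 32 df (critical value 2.037).

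| R² | SE ratio | Effective critical value | Unadjusted alpha | Noncentrality | Unadjusted power | Adjusted power |
|---|---|---|---|---|---|---|
| 0 | 1.00 | 2.032 | 5.0% | 2.40 | 64.5% | 64.3% |
| 0.10 | 1.05 | 2.142 | 3.9% | 2.53 | 65.2% | 68.9% |
| 0.20 | 1.12 | 2.272 | 3.0% | 2.68 | 66.0% | 74.0% |
| 0.30 | 1.20 | 2.429 | 2.1% | 2.87 | 67.0% | 79.4% |

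The unadjusted columns are approximations. A simulation of 40,000 trials per cell, with four strata balanced across arms, agrees for R² = 0.10, 0.20 and 0.30. Unadjusted alpha was 3.9%, 2.8% and 1.9%; unadjusted power 64.8%, 65.2% and 65.8%; adjusted power 68.8%, 73.8% and 79.2%. Adjusted alpha stayed at 5.0% to 5.1%. At R² = 0 power was 64.5% unadjusted and 64.3% adjusted.

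**Step 3: the mixed model that the plan describes.** Two hundred trials were simulated with 18 per arm, two visits, complete data, residual SD 0.7 per visit and a level effect of 1 for each factor.

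| Gender and age affect | Model as stated | Plus main effects | Plus gender-by-time and age-by-time | Empirical SD of estimate |
|---|---|---|---|---|
| Level only | 0.327 | 0.327 | 0.326 | 0.322 |
| Level and change (0.8 each) | 0.384 | 0.384 | 0.326 | 0.322 |

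The three model columns are mean standard errors of the group-by-time term. In the second row each factor adds about 0.8² × 0.25 = 0.16 to the variance of change, against residual 2 × 0.7² = 0.98. R² is then roughly 0.32/1.30 = 25%.

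Three results follow.
- With effects on level only, the stated model's standard error is already right, because a constant participant effect cancels from the change.
- With effects on change, it is too large by 0.384/0.326 = 1.18 against the time-interaction model, or 0.384/0.322 = 1.19 against the empirical SD.
- Main effects alone leave it as it was (largest difference below 0.00001). Point estimates were identical across the three models.

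**The case against.** The strongest reply is that the primary contrast is a within-participant change, so gender and age matter only if they predict that change, and the documents do not say that they do. The Introduction's deficiency rates (14% of males, 10% of females) and the PSS-10 norms in Appendix 6 (12.1 for males and 13.7 for females; 11.9 to 14.2 across age groups) describe levels. They make the factors plausible predictors but say nothing of 28-day change. This stands, and it is why the point is conditional and R² is given as a range.

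It can also be said that the adjusted models the plan mentions might include gender and age. They might. But the sentence commits to no variable and does not rank the adjusted result against the unadjusted one, so it does not close the gap.

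Finally, the unadjusted test is valid, if conservative, and the low power at 18 per arm is a sample-size matter that exists with or without covariates. Both are true. Adjustment would bring power to 80% only if the factors explained slightly more than 30% of the variance in change, so it is no substitute for correcting the sample size.

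**Conclusion.** The design and the stated analysis do not match: two factors are used to randomise and neither is committed to in the between-group model. If they explain 10% to 30% of the variance in change, the standard error is overstated by about 5% to 20%, true alpha is about 4% to 2%, and about 4 to 13 points of power are forgone. If they explain nothing, nothing is forgone, and adjusting would cost about 0.2 points. These sizes rest on the assumed R², arms balanced within strata, complete data and a linear model.

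A reader might infer more: that the standard errors are certainly overstated, or that the benefit of stratifying is lost. The documents support neither. The first depends on an association with change that they do not quantify. On the second, the arms remain balanced on both factors and the estimate remains unbiased; only the gain in precision is at risk. This is a free improvement and not an error that invalidates the analysis.

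**What to change.** In Statistical Methodology, prespecify gender and age in the primary and secondary between-group models in a form that acts on change. Either of these would do:

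- keep the mixed model and add gender-by-time and age-by-time terms with their main effects; or
- analyse the post-baseline value or the change by ANCOVA, with baseline, gender and age as covariates.

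Adding gender and age to the mixed model as main effects only is not enough. State whether age enters in the bands used for stratification, which should then be given, or as a continuous variable. Say that this adjusted model is primary, name any other moderators, and label those analyses exploratory.

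The cost is a change of wording before unblinding and about two degrees of freedom for the two-visit primary outcome. It is more if age is banded into several groups, or for the questionnaires, which have three visits. Both variables are already collected on the Health Screening Questionnaire (Appendix 3).

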# STUDY DURATION

Subject Participant Duration: 28 days

---

# NUMBER OF PARTICIPANTS

Number of Participants: Approximately 36 total (18 in each arm)

---

# INTRODUCTION

Vitamin C, also known as ascorbic acid, is a water-soluble essential nutrient that plays a multifaceted role in human physiology. Unlike many animals, humans lack the enzyme L-gulonolactone oxidase needed to synthesize it endogenously, so we must obtain it through diet or supplementation.

The body relies on vitamin C for several crucial functions to maintain healthiness. It acts as a cofactor for several enzymatic reactions, such as the biosynthesis of collagen, synthesizing L-carnitine, a non-enzymatic and potent antioxidant, enhances non-heme iron absorption in the gut, and supports immune function through modulating white blood cell activity.

Although Vitamin C is associated with a number of important processes, humans require external sources of Vitamin C to maintain internal levels. Dietary intake is obtained through fruits and vegetables, but this method of consumption may fall short due to the modern diets high in processed foods, food insecurity, or limited access to fresh produce. Further, factors like smoking, chronic stress, infections, pollution, etc. can increase oxidative stress, thus reducing vitamin C levels.

In fact, a considerable number of children and adults in the United States are vitamin C deficient or depleted. The Third National Health and Nutrition Examination Survey categorized vitamin C levels according to internationally established limits: deficiency (less than 11  $\mu\text{mol/L}$ ), depletion (11–28  $\mu\text{mol/L}$ ), or normal (more than 28  $\mu\text{mol/L}$ ). Overall, 14% percent of males and 10% of

females were vitamin C deficient. Another 20% of males and 17% of females were found to be depleted in vitamin C.

Dietary supplementation with Vitamin C has been shown to enhance the body's antioxidant capabilities, support healthy immune functioning, cognition, stress resistance, and maintain Vitamin C stores in preclinical and early clinical studies. Furthermore, the combination of bioflavonoids may have an additive effect for supporting these functions. Qualia Vitamin C+ is a novel multi-ingredient formulation developed to enhance the body's Vitamin C reserves, decrease oxidative stress, support immune function, and promote systemic health. It contains a strategic blend of Vitamin C (from a blend of liposomal vitamin C, minerals ascorbates, and fruit extracts), bioflavonoids, and ferulic acid, designed to optimize vitamin C status and provide comprehensive support for metabolic processes underlying healthy responses to oxidative stress and immunity.

The primary aim of this randomized, double-blind, placebo-controlled parallel trial is to compare the effects of a Qualia Vitamin C+ formulation on blood Vitamin C levels in healthy adult participants over a 28-day intervention period. Secondary objectives include evaluating the impact of supplementation on cognition, stress, and immunity, as reflected by changes in scores on the PROMIS Cognitive Function - Short Form 8a, the Perceived Stress Scale-10, and the Single-item Assessment of Immune Fitness, as well as characterizing the safety and tolerability profile and overall participant experience of the formulation.

---

## METHODS

### Study Design

Design: Randomized Double-Blind Placebo-Controlled Parallel Trial (2 arms) with 1:1 allocation, stratified by gender and age.

Arms: (1) Qualia Vitamin C+, and (2) Placebo

### Outcome Measures

Uta Labs Vitamin C Test [Note: Should be done following an overnight fast. For more information see <https://www.ultalabtests.com/test/vitamin-c-test>]

PROMIS Cognitive Function - Short Form 8a

Perceived Stress Scale-10

Single-item Assessment of Immune Fitness

Adherence Check-In

Overall Experience Questionnaire

Safety and Tolerability Survey

Follow-Up Questionnaire

## Assessment Procedures

All protocol-required laboratory tests will be ordered and funded by Qualia Life Sciences. Participants will not be responsible for any costs. Blood vitamin C levels will be measured via blood draws through Ultra Labs, which uses licensed blood draw centers operated by Quest Diagnostics. The Vitamin C test measures the concentration of ascorbic acid in the blood. It provides valuable information about a person's Vitamin C status, indicating whether they have sufficient levels of the vitamin, are deficient, depleted, or have normal levels. The test also helps monitor the effectiveness of supplementation. This test requires a 1 ml frozen serum sample. While the exact blood draw volume may vary slightly, labs typically collect between 2.5 and 5 ml of whole blood when 1 ml of serum is needed to ensure enough sample for testing and backup. We anticipate no more than 6 mL per visit, with a total blood volume not exceeding 12 mL over 5 weeks. These estimates are based on specimen requirements from Ultra Labs (when specified) and other similar laboratory services. The other measures include standardized electronic questionnaires (PROMIS Cognitive Function - Short Form 8a, Perceived Stress Scale-10, Single-item Assessment of Immune Fitness, Overall Experience Questionnaire, Safety and Tolerability, and adherence check-ins) will be administered through the Qualia Life Sciences survey platform. Laboratory Vitamin C test results will be securely transmitted from the testing laboratory via encrypted email in spreadsheet format, eliminating the need for manual data entry. Upon study completion, participants will receive their personal Vitamin C results; however, individualized interpretation will not be provided.

---

## Inclusion / Exclusion Criteria

Inclusion criteria:

Provide voluntary, written, informed consent to participate in the study.

Agree to provide a valid cell phone number and are willing to receive communications through text.

Can read and write English.

Willing to complete questionnaires, records, and diaries associated with the study.

Healthy male and female participants aged 25 years or older.

Willing to go to an Ulta Labs Patient Service Center location for a Blood Vitamin C Test (baseline and Day 29) and located within a convenient distance of participating locations. [Note: The services offered by Ulta Lab Tests are available only in the United States and not to residents of the states of New Jersey, New York, and Rhode Island.]

Willing to avoid starting new or stopping any existing dietary supplements throughout the study.

Exclusion criteria:

Women who are pregnant, breastfeeding, or planning to become pregnant or start breastfeeding during the trial.

Known food intolerances/allergy to any ingredients in the product.

Having any of the following conditions: Psychiatric conditions, neurologic disorders, endocrine disorders, cancer.

Having had a significant cardiovascular event in the past 6 months.

Taking MAO inhibitors, SSRIs, or any other psychiatric or neurological medicines  
On immunosuppressive therapy.

Adults lacking capacity to consent.

---

## Participant Recruitment

Participants will be recruited via an online recruitment platform. Interested individuals will complete a prescreen survey to determine eligibility. The online recruitment platform will include a description of the purpose of the study and the prescreen survey, along with an explanation of how the information collected in the survey will be used and who will have access to it. Eligible participants will be contacted to discuss the intervention and obtain Institutional Review Board (IRB)-approved informed consent. Online consent will be obtained from all participants. Following consent, the supplement will be delivered to their specified address.

---

## Randomization And Blinding

Participants will be randomized in a 1:1 ratio to one of two study groups: Qualia Vitamin C+ or placebo. To maintain double-blinding, a designated Qualia Life Sciences staff member independent of the research team will assign and label all study products as A or B. Both participants and study personnel will remain blinded to group assignments until study completion. Unblinding will occur only after all study data have been collected and finalized.

---

## Study Product

Active Products: Qualia Vitamin C+

Placebo: Contains inert rice powder in a vegetable/cellulose capsule.

Dosage Instructions: Participants will take two capsules of their assigned product daily in the morning, with or without food, for 28 consecutive days.

Supply: Participants will receive a 28-day supply (56 capsules) of their assigned intervention.

---

## Study Schedule

Days 1-28 are when participants will take the test formulas or placebo.

Screening (prior to enrollment (Day -21 to -15): Complete online prescreen questionnaire and provide electronic informed consent.

Baseline Assessments (Day -14 to -7):

1. Conduct Ulta Labs Vitamin C Test
2. Complete PROMIS Cognitive Function - Short Form 8a
3. Complete Perceived Stress Scale-10
4. Complete Single-item Assessment of Immune Fitness
5. Complete Safety and Tolerability survey

Note: Successful completion of baseline assessments and conformation of lab draw are required to ship a participant the study product.

Day 7 Assessments: Complete Safety and Tolerability survey.

Day 14 Assessments:

1. Complete PROMIS Cognitive Function - Short Form 8a
2. Complete Perceived Stress Scale-10
3. Complete Single-item Assessment of Immune Fitness
4. Complete Safety and Tolerability survey

Day 21 Assessments: Complete Safety and Tolerability survey.

Day 29 Assessments:

1. Conduct Ulta Labs Vitamin C Test
2. Complete PROMIS Cognitive Function - Short Form 8a
3. Complete Perceived Stress Scale-10
4. Complete Single-item Assessment of Immune Fitness

## 5. Complete Safety and Tolerability survey

Note: Participants should have blood drawn the day after their last supplement dose (ideally following an overnight fast and about 18–24 hours after their last dose of the supplement or placebo). This better reflects steady-state or trough plasma vitamin C, less influenced by the acute post-dose spike, and is the preferred approach in clinical and pharmacokinetic research to evaluate chronic supplementation effects, sustained tissue saturation, and baseline improvement. It is fine to have the participants complete the questionnaires on this same day (29) rather than day 28.

Follow-Up (Day 34-36): Complete post-study exit questionnaire.

Check-in Schedule: Day 1, 3, 7, 14, 21, 28

Note: Participants will complete regular check-in surveys to assess adherence and safety throughout the active supplementation period.

---

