## Appendix 2: Check-in

1. How many days this week (past 7 days) did you take the product?
2. How many capsules did you usually take each day?
3. What time during the day did you usually take the product?
4. Did you usually take the product with an empty or full stomach?
5. Have you noticed any side effects from taking the product?
6. Is there anything you would like to say?

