### Health and Medical History

1. Are you currently taking any prescription or over-the-counter medications, not including vitamins or herbal supplements? ☐ Yes ☐ No  
If yes, please list: \_\_\_\_\_

2. Are you currently taking any prescription psychiatric or neurologic medication (including MAO inhibitors or SSRIs)?

Examples: phenelzine, tranylcypromine, sertraline, fluoxetine, lithium, valproate, carbamazepine.

☐ Yes ☐ No

3. Are you currently on immunosuppressive therapy?

Examples: Calcineurin inhibitors, mTOR inhibitors, Antimetabolites (antiproliferatives), Corticosteroids, Alkylating agents (cytotoxic immunosuppressants), Biologic agents (monoclonal antibodies & fusion proteins).

☐ Yes ☐ No

4. Do you have any known food allergies or intolerances? ☐ Yes ☐ No

If yes, please specify: \_\_\_\_\_

5. Do you have any of the following medical conditions? (check all that apply)

- ☐ Psychiatric conditions (e.g., depression, anxiety, bipolar disorder)  
☐ Neurologic disorders (e.g., epilepsy, seizure disorders, Parkinson's disease, multiple sclerosis)  
☐ Endocrine disorders (e.g., diabetes, thyroid disorders, adrenal disorders)  
☐ Cancer (active, under treatment, or treated within the past 5 years)

6. Have you experienced a significant cardiovascular event in the past 6 months (e.g., heart attack, stroke, coronary bypass, angioplasty)? ☐ Yes ☐ No

7. Are you pregnant, planning to become pregnant, or currently breastfeeding? ☐ Yes ☐ No

8. Please use the space below for any other health information you believe is relevant:

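### The trough-timing rule for the vitamin C draw counts only from the study product and only at Day 29, so a participant's own vitamin C can raise either primary sample

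*Combined protocol and SAP*

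**What the plan says.** The Study Schedule note after the Day 29 assessments sets the timing: "Participants should have blood drawn the day after their last supplement dose", ideally fasting and "about 18–24 hours after their last dose of the supplement or placebo". It gives the reason as well: "This better reflects steady-state or trough plasma vitamin C, less influenced by the acute post-dose spike".

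The baseline draw appears in the same section under "Baseline Assessments (Day -14 to -7" days, with no interval from any supplement.

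The Outcome Measures section says of the vitamin C test: "Should be done following an overnight fast". This is a general note on the test, so it covers both draws. It does not mention supplements.

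The inclusion criteria require participants to be "Willing to avoid starting new or stopping any existing dietary supplements throughout the study". No criterion excludes people who take vitamin C or a multivitamin.

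Own use is not captured elsewhere. The medication question in the Health Screening Questionnaire (Appendix 3) is worded "not including vitamins or herbal supplements". The check-in (Appendix 2) asks "What time during the day did you usually take the product", which concerns the study product only.

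**The concern.** The protocol names the acute post-dose rise as the thing to avoid, but guards against it for one source of vitamin C at one of the two visits. A participant can keep to the fast, meet the interval from the study capsules and continue an existing vitamin C supplement as required, yet swallow that supplement with water shortly before either draw. The sample can then show the kind of rise that the note is meant to exclude.

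The primary outcome is a change between two single draws. If a participant's own-dose timing differs between the visits, the change score carries a component, up or down, that has nothing to do with the study product. In a trial of about 36 people this costs precision in the between-group comparison and in the secondary within-group vitamin C objective. Because neither own use nor its timing is recorded, it could not be examined afterwards.

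**Working it through.** **Reading the rules together**

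| Rule | Baseline draw | Day 29 draw | Covers own vitamin C? |
|---|---|---|---|
| 18–24 hour interval | no | yes (ideally) | no, study product only |
| Overnight fast | yes | yes | not mentioned |
| No starting or stopping of supplements | yes | yes | yes, it keeps users on them |
| Recording of own intake time | none | none | no |

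No visible rule sets a time between own vitamin C and either draw.

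**The plan's own power figure**

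Inputs from the Statistical Methodology and Number of Participants sections: d = 0.80, two-tailed 0.05, 80% power, 18 per arm. A two-sample t-test needs 25.5, so 26 per arm, or 52 in total. With 18 per arm (34 df, noncentral t) the power is 64.5%. The stated 80% is therefore not reproduced. That is a separate matter; here 64.5% is simply the starting point.

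**Illustration of the added noise**

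Assumptions, none given in the documents:
- SD of change without the extra component: 20 µmol/L. The true difference is then 0.80 × 20 = 16 µmol/L.
- p = share of participants taking their own vitamin C.
- s = post-dose rise in µmol/L.
- q = chance that a user's draw follows that day's own dose, equal at both visits and independent between them.

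For a user, the rise at Day 29 minus the rise at baseline has mean 0 and variance 2q(1−q)s². Over the sample:

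- added variance = p × 2q(1−q) × s²
- new SD = √(400 + added variance)
- new d = 16 / new SD

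| p | s | q | Added variance | New SD | d | Power, 18 per arm |
|---|---|---|---|---|---|---|
| – | 0 | – | 0 | 20.00 | 0.80 | 64.5% |
| 0.2 | 20 | 0.5 | 0.2 × 0.50 × 400 = 40 | 20.98 | 0.76 | 60.4% |
| 0.2 | 20 | 0.1 | 0.2 × 0.18 × 400 = 14.4 | 20.36 | 0.79 | 63.0% |
| 0.3 | 40 | 0.5 | 0.3 × 0.50 × 1600 = 240 | 25.30 | 0.63 | 45.4% |
| 0.3 | 40 | 0.1 | 0.3 × 0.18 × 1600 = 86.4 | 22.05 | 0.73 | 56.2% |

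q = 0.5 maximises 2q(1−q), so those rows are the upper end for each p and s. If p = 0, or if each user's timing is the same at both visits, the added variance is zero.

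**Within-group change.** The interval widens in proportion to the SD: 20.36/20 = 1.02 to 25.30/20 = 1.26, that is, by 2% to 26%.

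**Chance imbalance.** If one arm has k more post-dose draws than the other at one visit, the group difference shifts by k × s / 18. One extra draw with s = 20 gives 1.1 µmol/L. Three with s = 40 give 6.7 µmol/L, against the assumed true difference of 16 µmol/L.

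**The case against.** **The fast already deals with it.** It helps: an overnight fast makes a dose with breakfast less likely, and this is why a low q such as 0.1 is plausible. But the fast does not bar a capsule with water, and the Day 29 note lists fasting and the 18–24 hours as two separate conditions. The plan itself does not treat fasting as sufficient.

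**Randomisation deals with it.** This stands as far as systematic bias goes. A reader might infer that the treatment comparison is biased; in a randomised, blinded trial the documents do not support that. Noise and chance imbalance remain.

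**The size is speculative.** This also stands. The documents give no share of users, dose, rise or SD of change. The plan's d is already standardised, so an SD used for planning might include some background-supplement variation, and adding variance to it could then count that twice. Habitual users may also repeat their timing, which shrinks the effect.

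**Excluding vitamin C users would remove the problem.** True. The point matters because the protocol keeps them in. If they stay and are merely identified, the timing gap persists.

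**Instructions may exist elsewhere.** The fasting note refers readers to the laboratory's test page, and the consent pages are not in the review copy. The gap is established only for the text available.

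**Conclusion.** The gap is real in the text. The timing rule does not cover all vitamin C sources or both visits, so either primary sample can show a post-dose rise. The consequence is avoidable noise and possible chance imbalance in the between-group change, and a wider interval for the within-group change. Under the stated assumptions the power loss runs from about 1.5 points (64.5% to 63.0%) to about 19 points (64.5% to 45.4%), and it is zero with no users or identical timing. These figures also assume the same chance of a post-dose draw at both visits; nothing in the documents says otherwise.

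Three stronger readings are not supported:
- That the samples do show an acute peak. The documents establish only that they can.
- That the change becomes uninterpretable. The secondary objective is a within-group comparison, and the Assessment Procedures section says that individual results will not be interpreted for participants. Random timing makes the group estimate less precise, not meaningless.
- That this explains the gap between the stated 80% and 64.5%. That gap is present before any own-supplement effect.

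This is an inexpensive improvement worth making, not a flaw that undermines the trial.

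**What to change.** Reconcile the Outcome Measures fasting note, the supplement criterion, the baseline schedule and the Day 29 note, so that a single draw-timing condition applies at both baseline and Day 29 and covers every source of vitamin C:

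- Schedule each draw before that day's own vitamin C-containing supplement.
- Keep the interval from the last own intake the same at both visits, and as close to the protocol's stated 18–24 hours as feasible. A condition limited to the morning of the draw is not enough: an own dose at 10 p.m. before an 8 a.m. draw leaves only 10 hours.
- Record the time of last own intake at each draw, and examine departures in a sensitivity analysis.

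The condition governs sampling and does not require anyone to start or stop a supplement, so it is compatible with the inclusion criterion. The cost is slight inconvenience in scheduling on two days and one extra recorded item. No additional visit or blood sample is needed.
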